Title: Efficacy of the Quell Wearable Device for Chronic Low Back Pain

NCT# 02944513

Date: July 1, 2016

STUDY PROTOCOL - METHODS

This trial is registered at ClinicalTrials.gov (NCT02944513). The Human Subjects Committee of Brigham and Women's Hospital (BWH) will approve the study procedures and written informed consent will be obtained from every participant. Flyers will be distributed about this trial and subjects will be recruited consecutively as they respond to the flyers. We will recruit patients with a primary complaint of chronic low back pain and randomize each of the subjects to one of two treatment conditions: 1) the hTENS device or 2) treatment-as-usual control (no device) using a random number table (<https://www.graphpad.com/quickcalcs/randomize1.cfm>). All participants will be adults age 21 or older and diagnosed with axial musculoskeletal or discogenic back pain with or without radiculopathy. There will be a number of other inclusion criteria: (1) participants will need to own a compatible smartphone, either Android or iPhone, (2) they will have to have evidence of chronic pain for over 6 months and average ≥ 4 on a 0-10 pain intensity scale, and (3) they will need to understand and speak English. Study exclusion criteria will include (1) diagnosis of cancer, (2) evidence of osteomyelitis, (3) a psychiatric disorder judged to interfere with the study (e.g., psychosis or delusional disorder), (4) an active substance abuse disorder (e.g., cocaine or heroin use), (5) surgery scheduled within 3 months, (6) pregnancy, (7) an implanted device (e.g., pacemaker), and (8) any unstable systemic illness judged to interfere with treatment.

During the 3-month study period all participants will be discouraged from making changes in their pain management regimen.

We will employ the use of a smartphone pain app in this study,^{16,17} which was designed to collect daily assessment data as well as demographic and medical information. It was devised to help monitor daily patient progress over the period of the trial. All subjects will be informed how to find the apps ('Quell Relief' and 'BWH Painapp' either on the App Store or Google Play) and will be assisted in downloading the apps, if assistance is needed. The pain app has built-in daily reminders for the user with push notification to complete daily assessments as well as 2-way messaging to connect with study staff.

Patients will be randomized to either the Experimental group with use of a hfTENS or Control group with treatment as usual. Both groups will be asked to use the smartphone pain app to monitor their daily assessments. All subjects will complete a packet of validated questionnaires and will be followed for 3 months. All participants will sign an informed consent form and will be given assistance in downloading the apps by a research assistant (RA) who will answer any questions and help to manage any problems that the individuals might encounter. All participants will be also administered QST at baseline.^{11,12}

Patients randomized to the experimental group (hfTENS) will be encouraged to use the device at least two hours every day. Tracking of use of the device will be available electronically through the hfTENS app. All demographic and daily pain assessment data will be stored on a secure server (Veracode tested) and messages will be sent via the 2-way messaging pain app program to help track use of the device and

to address any problems that the subjects might encounter. All subjects will be also asked to complete post-intervention mailed assessments after 3 months and return the completed assessments in pre-addressed stamped envelopes. Each subject will be compensated \$25 at baseline and \$50 at study completion upon receipt of their completed assessments. All subjects will be allowed to keep their hFTENS device at the end of the study. Those subjects assigned to the Control condition will be offered a hFTENS device at the end of the 3-month trial period.

Brief Quantitative Sensory Testing

Pressure pain thresholds (PPTs) will be assessed using a standard manual pressure algometer (*Wagner Force Ten Digital Force Gage; www.wagnerinstruments.com*).

PPTs will be evaluated at the trapezius muscles bilaterally and at the wrists bilaterally (four sites) by a trained and experienced RA. A 0.5 cm² probe covered with a rubberized pressure-transducing material will be applied twice to each site to measure PPTs. Mechanical force will be gradually increased until the subject verbally indicates to the tester that the pressure is “painful.” Temporal summation of mechanical pain will be assessed using weighted pinprick stimulators at each of the metacarpophalangeal joints of the middle fingers with a *Touch-Test Sensory Evaluator*

(*www.ncmedical.com*).¹⁴ The subjects will be instructed to indicate which of the probes produced a painful sensation (usually the 128 or 256 mN gauge) and this stimulator will be used to apply a series of 10 sequential stimuli at the rate of 1 per second to the dorsum of the hand. The RA will ask the subjects to indicate their perceived level of painfulness of the first, fifth, and tenth stimulus. The degree of mechanical temporal summation will be determined by the increase in pain (as rated by the subject) between

the first and last stimulus. We and other groups have frequently employed these QST procedures in prior studies among patients with a broad array of musculoskeletal chronic pain conditions.^{11,12,18}

Patient Measures

Participants will complete measures recommended by the Initiative on Methods, Measures, and Pain Assessment in Clinical Trials (IMMPACT)¹⁹ as primary outcomes. All participants will be asked to complete a series of baseline questionnaires. Identical questionnaires will be mailed to the subjects for completion after 6 weeks and again after 3 months. All subjects will be supplied with self-addressed stamped envelopes to mail back their completed questionnaires. The following measures will be administered to the study patients: (1) The Brief Pain Inventory (BPI).^{20,21} It has been shown to have excellent reliability and validity among samples of chronic pain patients; (2) The Pain Disability Inventory (PDI).²² This is a 7-item questionnaire designed to assess activity-related disability in performing household chores, recreational and social activities, work-related and sexual activities, general activities of daily living, and life-supporting behavior. It has been shown to have excellent reliability and validity; (3) The Pain Catastrophizing Scale (PCS).^{23,24} This is an instrument that examines the propensity for recurring intrusive ruminating thoughts. Persons scoring high on this scale tend to magnify and amplify their pain and show signs of helplessness. It has good psychometric properties with adequate reliability and validity; (4) The Hospital Anxiety and Depression Scale (HADS).^{25,26} This is a valid and reliable measure of anxious and depressive symptoms over the past week. The HADS has been used extensively in

clinics to assess mood and has been shown to have an optimal balance between sensitivity and specificity.

Once a week the subjects will be called by the RA and asked to rate their current progress on a 0=no pain/no interference to 10=worse possible pain/extreme interference on the following items: 1) current pain intensity, 2) average pain intensity, 3) pain interference on activities of daily living, social activities, outdoor and recreational activities, sleep, appetite, work ability, and 4) anxiety, depression and irritability from 0=stable mood to 10=worse possible mood. All questions were developed and standardized from a previous study.²⁷ All subjects will be asked about their current pain medications and all changes in prescription pain medications will be noted. Participants assigned to the Experimental group will be also asked which leg they used the hTENS on over the past week and all subjects will be given the opportunity to share any additional thoughts about the study.

At 3-month post-treatment all patients will be sent a packet of the baseline questionnaires to complete again and return by self-addressed stamped envelopes. Those in the Experimental group will be also asked to respond to a 14-item helpfulness questionnaire designed to investigate the perceived benefit of the hTENS. Those in the Control group will complete helpfulness questions only about the study and perceived helpfulness of the pain app. All items, which were developed in a prior study,¹⁸ and adapted from a previously validated measure,²⁸ will be rated on a 0 to 10 scale (e.g., not at all helpful to very helpful) and assessed helpfulness, bothersomeness, ease of use, how often they used the device, and whether the user was willing to use the hTENS in the future.

Statistical Analysis Plan

The aim of this study is to establish the safety, efficacy, feasibility, and tolerability of the hfTENS device for use among chronic back pain patients. We will use an intent-to-treat analysis and all variables will be assessed using univariate and multivariate analyses to establish group differences at baseline and follow-up. Although this will be designed as a preliminary study, power calculations, as outlined by Cohen,²⁹ will be performed to determine the probability of detecting clinically significant differences between treatment groups in the primary area of measurement: pain intensity. These calculations will assume a two-tailed test and alpha level of 0.025 confirming the hypotheses that the Quell would be associated with general overall improvement (e.g., more pain relief). A more rigorous $p < 0.025$ significance level will be established rather than $p < 0.05$ because of the multiple observations. The power analyses is expected to reveal that a sample size of 60 subjects (30 per treatment group), gives the study a >80% probability of detecting a 1.5-point group difference on a 0-10 rating scale. Depending on the nature of the variables, chi-square, t-tests, and logistic regression analyses will be conducted. We also will examine and report on the qualitative responses of the participants in using the hfTENS. Group differences will be assessed using repeated measures ANOVA and preliminary mixed linear regression model analyses, as appropriate.

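### The primary outcome is not fixed, and the 0.025 level is sure to hold 5% only for up to two tests, a limit the plan never sets

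*Combined protocol and SAP*

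**What the plan says.** Two sections bear on what is primary.

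- **Patient Measures** has participants complete measures recommended by the Initiative on Methods, Measures, and "Pain Assessment in Clinical Trials (IMMPACT)¹⁹ as primary outcomes". Four questionnaires follow: BPI, PDI, PCS and HADS. They are given at baseline and mailed "for completion after 6 weeks and again after 3 months". The same section describes a telephone contact: "Once a week the subjects will be called by the RA and asked to rate their current progress". Its items include "1) current pain intensity, 2) average pain intensity", each rated 0 to 10. The Methods text also has both groups record daily assessments in the pain app.
- **Statistical Analysis Plan** sets the power calculation "in the primary area of measurement: pain intensity". It expects more than 80% power for a 1.5-point group difference on a 0-10 scale with 30 per group, two-sided at 0.025.

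On multiplicity the SAP says only: "A more rigorous $p < 0.025$ significance level will be established rather than $p < 0.05$ because of the multiple observations". On the analyses it says that "all variables will be assessed using univariate and multivariate analyses to establish group differences at baseline and follow-up". After listing chi-square, t-tests and logistic regression, it adds: "Group differences will be assessed using repeated measures ANOVA and preliminary mixed linear regression model analyses, as appropriate".

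**The concern.** One section uses the plural, primary outcomes, for a battery of four questionnaires. The other singles out pain intensity, which is an area and not yet an endpoint. Four sources could supply it: the BPI, the weekly current rating, the weekly average rating and the daily app assessments. The SAP does not say which one decides, when, or by which of the listed analyses.

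The tightened significance level is justified by multiple observations but tied to no number of tests. A reader therefore cannot tell which result would establish efficacy or what false-positive rate that claim would carry. The deciding score and analysis could also be picked after the data are seen.

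**Working it through.** **Inputs from the documents.** Two-sided level 0.025 per test, 30 per group and a 1.5-point difference (SAP); four questionnaires and two follow-up mailings (Patient Measures).

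**Assumptions, not in the documents.**
- A 5% familywise target, inferred from the SAP's comparison with p < 0.05.
- Any one significant primary outcome counts as efficacy.
- One score per questionnaire.
- A common correlation ρ between test statistics, shown at 0.5, 0.7 and 0.9.
- The SD of the pain score.

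**1. The plan's own figure.** The expected power above 80% cannot be reproduced as a single number, because no SD is given. By the noncentral t (58 df), 30 per group and 1.5 points at two-sided 0.025 give 80% at an SD of about 1.84. They give 82.0% at SD 1.8 and 72.6% at SD 2.0. The statement is attainable, and the error-rate check below does not depend on it.

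**2. What 0.025 guarantees.** Under any dependence, the chance of at least one false positive in k tests is at most k × 0.025:
- k = 2: 2 × 0.025 = 5%
- k = 4: 4 × 0.025 = 10%
- k = 8: 8 × 0.025 = 20%

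Two is the largest number of tests for which 5% is assured.

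**3. Error rates by number of tests.** For independent tests the chance is 1 − 0.975^k. For k equally correlated normal statistics with c = 2.2414 it is

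1 − ∫ φ(u) [Φ((c − √ρ·u)/√(1−ρ)) − Φ((−c − √ρ·u)/√(1−ρ))]^k du.

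| Situation | k | Independent | ρ = 0.5 | ρ = 0.7 | ρ = 0.9 | Upper bound |
|---|---|---|---|---|---|---|
| One pain score, one test | 1 | 2.5% | 2.5% | 2.5% | 2.5% | 2.5% |
| Two tests | 2 | 4.9% | 4.6% | 4.3% | 3.6% | 5% |
| Four questionnaires, once each | 4 | 9.6% | 8.3% | 7.0% | 4.9% | 10% |
| Four questionnaires, 6 weeks and 3 months tested separately | 8 | 18.3% | 13.9% | 10.6% | 6.4% | 20% |

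Simulating trials of 30 per arm with four t-tests gives 9.5%, 8.3% and 5.0% at ρ = 0, 0.5 and 0.9, in line with the third row.

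**4. Correlation needed to reach 5%.** Solving the same formula gives ρ of about 0.90 for four tests and about 0.95 for eight. Independence is unlikely for measures taken on the same patients, so the correlated columns are the more realistic ones.

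**The case against.** The strongest reply is that the SAP is the governing section and it does single out pain intensity. It powers a between-group difference of stated size on a 0-10 scale. It also says that group differences will be assessed by repeated measures ANOVA or mixed models. One group test from such a model is a single test at 2.5%, however many time points it spans. The Patient Measures phrase may describe what IMMPACT recommends and not rank this trial's outcomes. The plan never claims a 5% familywise rate, and never says that one significant measure is enough. Its hypothesis of overall improvement could mean a pattern across measures, and if all four had to succeed there would be no inflation. The study also calls itself preliminary.

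Much of this stands. The 5% target and the any-one-success rule are assumptions, and 0.025 is adequate for one or two tests. A reader might infer that the two sections flatly contradict each other, that the level fails on every reading, or that each weekly rating will be tested separately. The documents support none of these: the phrase is ambiguous, a single model test would be covered, and no week-by-week testing is proposed.

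What the reply does not supply is a commitment. The models are to be used as appropriate, beside univariate tests of all variables. No outcome is attached to them, and it is not said whether the overall group effect, the group-by-time interaction or a time-point contrast decides.

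**Conclusion.** The point holds in a limited form. The primary outcome is described in two ways that are not reconciled, and the narrower description still fixes no score, time point or deciding analysis. The 0.025 level assures 5% for at most two tests, and nothing in the plan holds the primary tests to two.

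If the four questionnaires are taken as primary, the stated level exceeds 5% unless the correlation reaches about 0.90 (one test each) or about 0.95 (both follow-ups tested separately). These figures rest on the assumed 5% target, the any-one-success rule, one score per questionnaire and equal correlations. A reader might take 9.6% or 18.3% as the trial's false-positive rate. That is not supported, because those are the independent-test values on one reading of an ambiguous plan.

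The consequence is moderate because the study is preliminary. It should still be fixed, since the SAP also aims to establish efficacy and to confirm its hypotheses.

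**What to change.** - **Patient Measures:** remove the description of the questionnaire battery as primary outcomes.
- **SAP, endpoint:** name one 0-10 pain-intensity score at 3 months as the single primary endpoint. The sponsor chooses among a BPI item or score, the weekly average rating and the daily app rating. If a weekly or daily rating is chosen, state which calls or days form the 3-month value.
- **SAP, deciding test:** name one contrast, the between-group difference at 3 months, adjusted for the baseline score, from a mixed model using all follow-ups.
- **SAP, level:** state that 0.025 is kept as a conservative level for that one test, or name the two tests it covers.
- **SAP, everything else:** make all other measures and time points secondary, reported with confidence intervals.

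**Cost.** Sample size, level and data collection stay as they are, but this is more than a wording change. It commits the analysis to one model and one time point and adds a baseline adjustment that the documents do not mention. Power for that contrast may differ from that of a repeated-measures average. The other measures can no longer be claimed as primary successes. Keeping 0.025 for a single test also gives up power relative to 0.05. For an unadjusted t-test with 30 per group and 1.5 points, power is 82.0% against 88.8% at an assumed SD of 1.8, and 72.6% against 81.5% at 2.0. The sponsor should say that this is accepted.

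### The analysis plan never commits to adjusting follow-up pain for the baseline pain score, so precision may be lost at no saving

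*Combined protocol and SAP*

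**What the plan says.** Under Patient Measures, "All participants will be asked to complete a series of baseline questionnaires" and "Identical questionnaires will be mailed to the subjects for completion after 6 weeks and again after 3 months". The set includes the Brief Pain Inventory, so each patient should have a baseline pain score and two follow-up scores on the same instrument.

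The Statistical Analysis Plan is one paragraph. It powers the study "in the primary area of measurement: pain intensity". On methods it makes three statements:

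- variables are to be examined by "univariate and multivariate analyses to establish group differences at baseline and follow-up";
- "Depending on the nature of the variables, chi-square, t-tests, and logistic regression analyses will be conducted";
- "Group differences will be assessed using repeated measures ANOVA and preliminary mixed linear regression model analyses, as appropriate".

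It names no covariate, model terms, primary time point or primary contrast. Neither the protocol nor the SAP says that follow-up pain will be adjusted for baseline pain.

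**The concern.** The methods listed treat the baseline score differently.

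- A t-test on the follow-up score ignores it.
- Repeated measures ANOVA with baseline as a time level treats it as one more outcome. The group main effect then averages in an occasion on which treatment can have had no effect. The group-by-time term behaves like a change score.
- A mixed model can adjust for baseline, through a covariate or a common baseline mean, but the plan does not say that it will.

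The qualifier that closes the sentence on ANOVA and mixed models leaves the choice open until the data are in hand. Testing for baseline group differences does not fill the gap. After randomisation such differences are due to chance, and a significance test does not remove their effect on the estimate.

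At stake is precision with 30 patients per arm, and an estimate that carries whatever baseline gap happens to occur. Randomisation keeps the unadjusted estimate unbiased on average, so this is not a claim of bias.

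**Working it through.** **Inputs from the SAP.** 30 per arm and a 1.5-point difference on a 0-10 scale. For alpha: "These calculations will assume a two-tailed test and alpha level of 0.025".

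**Inputs not in the documents (assumptions).** The SD of pain, and the baseline-to-follow-up correlation r, taken as 0.2, 0.3, 0.5 and 0.7. SDs are equal at all times unless stated.

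**1. The plan's own figure.** Power above 80% cannot be checked directly without an SD. Solving for the SD that gives exactly 80%:

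- normal approximation: 1.5 / (√(2/30) × (2.241 + 0.842)) = 1.88;
- noncentral t, 58 df: 1.84.

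I use 1.84 (unrounded 1.843), which takes the plan's power claim as just met by a t-test.

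**2. The 3-month score alone.** The standard error is √(2/30) = 0.258 times the SD of the quantity analysed:

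- t-test: SD;
- change score: SD × √(2(1 − r));
- baseline-adjusted (ANCOVA, 57 df): SD × √(1 − r²).

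At r = 0.5 the ANCOVA SD is 1.843 × √0.75 = 1.596. ANCOVA also pays a little for chance baseline imbalance: its variance rises on average by a factor 1 + 1/56. Both versions are shown.

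| Power, 3-month score | r = 0.2 | 0.3 | 0.5 | 0.7 |
|---|---|---|---|---|
| t-test | 80% | 80% | 80% | 80% |
| Change score | 58% | 64% | 80% | 96% |
| ANCOVA | 82% | 84% | 91% | 98% |
| ANCOVA, allowing for imbalance | 81% | 83% | 90% | 98% |

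The half-width of the 97.5% confidence interval is 1.10 points unadjusted. Adjusted, with the imbalance allowance, it is 1.08, 1.05, 0.96 and 0.79.

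A larger SD lowers every row but keeps the ordering. At SD 2.5 the t-test has 51%, and ANCOVA without the imbalance allowance has 56%, 65% and 83% at r = 0.3, 0.5 and 0.7.

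**3. Both follow-ups together.** Assume an effect of 1.5 at each and equal correlations. Variance factors for the mean of the two follow-ups are:

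- unadjusted: (1 + r)/2;
- change from baseline: (1 + r)/2 + 1 − 2r;
- baseline-adjusted: (1 + r)/2 − r².

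For repeated measures ANOVA over three occasions the group differences are 0, 1.5 and 1.5. The main effect is therefore 3.0/3 = 1.0, with SD × √((1 + 2r)/3). The interaction is F on 2 and 116 df with noncentrality 15 × 1.5 / (SD² × (1 − r)).

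| Power, both follow-ups | r = 0.2 | 0.3 | 0.5 | 0.7 |
|---|---|---|---|---|
| ANOVA group effect, baseline as a level | 78% | 72% | 61% | 52% |
| ANOVA group-by-time | 62% | 69% | 85% | 98% |
| Change in mean follow-up | 72% | 78% | 91% | 99% |
| Unadjusted mean follow-up | 96% | 94% | 91% | 87% |
| Baseline-adjusted mean follow-up | 97% | 97% | 98% | 99.8% |

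**4. The entry rule.** Patients must "average ≥ 4 on a 0-10 pain intensity scale", which may narrow the baseline spread.

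- If baseline SD falls to 1.25-1.5, the 3-month change score has 66-72%, 73-78%, 87-89% and 98% power. The gain from adjusting over a change score is then at most about 4 points at r of 0.5 or more.
- Restriction may also lower r. For a normal parent (mean 5.5-6, SD 1.84) cut at 4, r of 0.3, 0.5 and 0.7 becomes about 0.2, 0.4 and 0.6. At r = 0.2 to 0.4, ANCOVA with the imbalance allowance has 81% to 86%, a gain of about 1 to 6 points over a t-test.

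**5. Chance baseline gap.** The standard error of the baseline difference is 0.258 × SD: 0.323, 0.387 and 0.476 at SD 1.25, 1.5 and 1.84. The chance of a gap over 0.5 point is 12%, 20% and 29%. At a slope of 0.5, a 0.5-point gap moves an unadjusted comparison by 0.5 × 0.5 = 0.25 point, one sixth of the 1.5-point target.

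**The case against.** The best counter-argument is that the plan's efficacy comparison is longitudinal and may already use the baseline score. The t-tests appear in a general list, and the hypothesis is about improvement, which points to change or group-by-time rather than a main effect averaged over baseline. Against change-type analyses the gain shrinks as r rises: with both follow-ups at r = 0.7, group-by-time has 98%, change 99% and adjusted 99.8%. Where adjustment beats change scores by most (low r), it beats a t-test by little. No single r makes adjustment important against every alternative.

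That is fair on size, and the lowest row in the second table is one reading of the plan, not the only one. It does not remove the point. The plan does not say which reading is meant. Leaving that row out, power at r = 0.5 with both follow-ups still runs from 85% to 98%. In both tables, with equal SDs, adjustment is at least as powerful as every alternative at every r.

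Three further points stand in part.

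- SD and r are assumptions, so no loss specific to this trial is shown.
- The SAP calls the study preliminary. It nevertheless states an efficacy aim, an alpha and a power.
- The protocol also collects weekly telephone ratings and daily app data and does not say which supplies the primary pain score. Averaging 12 weekly ratings under the same assumptions gives variance factor (1 + 11r)/12 and unadjusted power of about 92% at r = 0.7, rising above 99.9% at r = 0.2. Adjustment still helps: at r = 0.7 the factor falls from 0.725 to 0.725 − 0.49 = 0.235.

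**Conclusion.** The concern holds. Nothing in the protocol or SAP commits to baseline adjustment, and following the plan as written can give a less precise answer than the data allow.

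The size depends on r and on which listed method would otherwise be used. Compared with a 3-month t-test, and allowing for chance imbalance, adjustment adds about 1 point of power at r = 0.2, 10 at r = 0.5 and 18 at r = 0.7. The entry rule makes the lower end more likely. Compared with a 3-month change score under equal SDs, it adds about 23 points at r = 0.2 and 2 at r = 0.7.

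These figures assume SD 1.84, complete data on 30 per arm, and equal correlations where two follow-ups are used. The direction does not depend on the SD: apart from the small imbalance allowance, the adjusted variance is 1 − r² times that of a t-test and, with equal SDs, (1 + r)/2 times that of a change score. The stated sample size is not made wrong, and the unadjusted comparison remains valid. It is a worthwhile improvement that should be made, not a flaw that invalidates the design.

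**What to change.** State in the SAP that the primary comparison is 3-month pain intensity with baseline pain as a covariate, whatever baseline balance is observed. Use either ANCOVA or the mixed model already planned, with the 6-week and 3-month scores as outcomes and the 3-month contrast named as primary. A mixed model with a common baseline mean for the two arms would serve about as well. Name the source of the pain score and take the baseline value from the same source. Report the adjusted difference with its confidence interval.

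Analyse each other questionnaire score in the same way with its own baseline. Present baseline characteristics descriptively, without significance tests, and do not let observed imbalance decide the model.

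The cost is a few lines of SAP text, one degree of freedom and the small allowance for chance imbalance shown above. No extra patients, visits or measurements are needed.

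### No single test of pain intensity is fixed; committing to a baseline-adjusted 3-month difference would make efficient use of ratings already collected

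*Combined protocol and SAP*

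**What the plan says.** The Statistical Analysis Plan names pain intensity as the primary area of measurement. On the error rate it says "These calculations will assume a two-tailed test and alpha level of 0.025", and on power that 60 subjects, 30 per group, "gives the study a >80% probability of detecting a 1.5-point group difference on a 0-10 rating scale". On the population it says "We will use an intent-to-treat analysis".

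On method it gives two sentences: "Depending on the nature of the variables, chi-square, t-tests, and logistic regression analyses will be conducted", and then "Group differences will be assessed using repeated measures ANOVA and preliminary mixed linear regression model analyses, as appropriate". Neither says which analysis of pain intensity is the test, which effect in a repeated measures ANOVA would be read, at which visit, or whether baseline pain is adjusted for.

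Pain is measured in several ways. Patient Measures lists the Brief Pain Inventory among the baseline questionnaires and says "Identical questionnaires will be mailed to the subjects for completion after 6 weeks and again after 3 months". The same section adds weekly calls that record "1) current pain intensity, 2) average pain intensity". The Methods add daily pain assessments through the app. Patient Measures also describes a set of recommended measures, in the plural, as primary outcomes, which does not sit easily with one primary area in the Statistical Analysis Plan.

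**The concern.** The listed analyses are not interchangeable. Treatment cannot affect the baseline visit, so an ANOVA group effect averaged over baseline and follow-up is diluted. A group-by-time test depends on how early the effect appears. A 3-month t-test avoids both problems but ignores the baseline rating. A 3-month comparison adjusted for baseline avoids both problems and uses that rating.

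At stake is how much power the trial gets from 60 subjects and data it already plans to collect, and whether the power statement refers to a defined comparison.

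**Working it through.** **Inputs from the Statistical Analysis Plan:** 30 per group, two-sided 0.025, difference 1.5 points, power above 80%.

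**Assumptions, not in the documents:** SD; the same SD and the same correlation r (0.3, 0.5, 0.7) at baseline, 6 weeks and 3 months; no loss unless stated; onset either early (effects 0, 1.5, 1.5) or gradual (0, 0.75, 1.5).

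**Step 1: the plan's own figure.** It cannot be reproduced because no SD is given, but it can be solved backwards. For a two-sample t-test with 58 df (noncentral t), 80% power needs a standardised difference of 0.8138, so SD = 1.5 / 0.8138 = 1.843. An unadjusted 3-month t-test therefore meets the claim if SD is at most about 1.84. The limit is 1.5 / 0.8600 = 1.74 with 27 per group (10% loss) and 1.5 / 0.9152 = 1.64 with 24 (20% loss).

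**Step 2: other comparisons at SD 1.843, 30 per group.**

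- ANOVA group effect over three visits. The averaged difference is (0 + 1.5 + 1.5)/3 = 1.0 (early) or (0 + 0.75 + 1.5)/3 = 0.75 (gradual). The SD of a subject's mean is SD × √((1 + 2r)/3) = 1.346 / 1.505 / 1.649.
- Group-by-time, F with 2 and 116 df. Noncentrality is (30/2) × Σ(δ − mean δ)² / (SD² × (1 − r)). The sum of squares is 1.5 (early) or 1.125 (gradual), giving 9.46 / 13.24 / 22.07 or 7.10 / 9.93 / 16.56.
- Baseline-adjusted 3-month difference. Effective SD is SD × √(1 − r²) × √(1 + 1/(2n − 4)) with 2n − 3 = 57 df, which gives 1.774 / 1.611 / 1.328. The last factor allows for chance baseline imbalance.

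| Power at r = 0.3 / 0.5 / 0.7 | Early onset | Gradual onset |
|---|---|---|
| Unadjusted 3-month t-test | 80 / 80 / 80% | 80 / 80 / 80% |
| ANOVA group effect, baseline included | 72 / 61 / 52% | 45 / 36 / 30% |
| Group-by-time | 69 / 85 / 98% | 54 / 71 / 92% |
| Baseline-adjusted 3-month difference | 83 / 90 / 98% | 83 / 90 / 98% |

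**Step 3: sensitivity of the adjusted comparison.**

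- SD, 30 per group: 76 / 84 / 96% at SD 2.0 (t-test 73%) and 55 / 64 / 82% at SD 2.5 (t-test 51%).
- Loss, SD 1.843: 78 / 86 / 96% with 27 per group (t-test 75%) and 73 / 81 / 94% with 24 (t-test 69%).
- Baseline uninformative (r = 0): 79%, against 80% for the t-test.

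**Step 4: form of the adjusted model.** A mixed model of all three visits with equal group means at baseline gives the same 3-month estimate as simple baseline adjustment when there is no loss. With 20% loss, half of it after 6 weeks, simulated power is 72.1 / 80.9 / 93.9%, against 72.5 / 81.2 / 94.0% for simple adjustment with 24 per group. The two are nearly equivalent here.

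**Step 5: a conditional power statement.** With 27 evaluable per group, the adjusted comparison has 80% power if SD is at most about 1.81 / 1.99 / 2.42 for r = 0.3 / 0.5 / 0.7.

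**The case against.** The plan never names an ANOVA group effect that pools the baseline visit, so the lowest figures describe an analysis it permits rather than one it announces. Its reference to differences at baseline and at follow-up could even suggest separate comparisons. A mixed model is already listed and could adjust for baseline, so the better analysis is unspecified, not excluded. This stands.

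The equal-SD assumption may also exaggerate the dilution. Entry requires average pain of at least 4, which narrows the baseline range. With an assumed baseline SD of 1.4 and follow-up SD of 1.84, the early-onset group effect has 79/69/60% instead of 72/61/52%. The same restriction may lower r and so shrink the gain from adjustment, which at r = 0.3 is only 3 points over the t-test. This stands too.

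The adjusted 3-month difference is not always the most powerful choice. With early onset, an unadjusted mean of both follow-ups would have 94% at r = 0.3 and about 91% at r = 0.5, though less than the adjusted test at r = 0.7. With gradual onset it falls to 60-74%.

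A reader might infer that the power claim is false. The documents do not support that: a two-tailed test of a 1.5-point difference reads naturally as a comparison of two means, and Step 1 shows when it reaches 80%. A reader might also infer that the test will be chosen after the results are seen, inflating the error rate. The plan does not say so, and it calls the study preliminary.

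What survives is that the plan aims to establish efficacy and sets a significance threshold for it, without saying which comparison that threshold applies to.

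**Conclusion.** The point holds as a recommendation to improve the analysis. No test, visit, rating or baseline adjustment is fixed for pain intensity, and a better comparison is available from data already planned.

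The powers are illustrations. They rest on an SD back-solved from the plan's own 80%, on assumed correlations and on equal SDs across visits. Neither the 30-98% spread across the ANOVA effects nor the 83-98% for the adjusted test is a property of 60 subjects. What does not depend on the SD is the ordering: the adjusted 3-month difference matches or beats the unadjusted 3-month t-test, apart from about 1 point of power when r is near 0, and it does not depend on when the effect appears before 3 months.

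**What to change.** Add to the Statistical Analysis Plan, for example: *The single primary test is the group difference at 3 months in [one named 0-10 pain intensity rating] from the mailed questionnaire, adjusted for the same rating at baseline, at two-sided 0.025, in all randomised subjects as assigned. Other tests of pain intensity are supportive.*

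- The sponsor names the rating. Average pain is the natural choice because the entry criterion uses it. Three months fits the schedule in Patient Measures: "At 3-month post-treatment all patients will be sent a packet of the baseline questionnaires to complete again".
- State one model. ANCOVA or the mixed model with baseline adjustment will do. The mixed model assumes loss is missing at random, and subjects with only a baseline rating add no information on the difference.
- Reconcile this with the set of measures that Patient Measures calls primary outcomes.
- Restate the power for this comparison as conditional on a stated SD, r and loss, for example with the SD limits in Step 5.

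The cost is wording only, with no added subjects, visits or data. The downsides are up to about 1 point of power if baseline pain does not predict 3-month pain, no freedom to choose the model later, and less power than a mean of both follow-ups if the effect is full by 6 weeks and r is low.
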